## **Study Population**

Eligible participants were adults with a diagnosis of diabetes mellitus and a non-healing DFU measuring greater than 1 cm^2 in area, without exposed bone or tendon. Full inclusion and exclusion criteria are shown in Table 1.

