## **Outcomes and Data Collection**

Baseline demographic data, medical history, comorbidities, current treatments, and wound characteristics were recorded at enrolment. Participants were evaluated weekly or biweekly for up to 24 weeks or until complete wound healing, whichever occurred first. At each visit, wound surface areas were measured and documented using standardized digital photography. Adverse events were assessed and documented at each visit. Debridement, when necessary, was performed as part of routine clinical care and recorded.

The **primary outcome** was the proportion of wounds achieving complete healing within 24 weeks. Complete wound healing was defined as full re-epithelialization without drainage or dressing requirements. Wound healing was assessed jointly by the treating plastic surgeon and wound care nurse. Due to resource constraints, independent blinded assessors were not employed.

**Secondary outcomes** included percentage reduction in wound area, wound recurrence rates, incidence and nature of adverse events, and the need for additional surgical intervention. Participants who achieved wound healing were followed at 2- and 12-weeks post-healing to monitor for recurrence or complications.

Unblinding of treatment allocation was permitted only in the case of a serious adverse event (SAE) in which treatment knowledge was required for patient safety. All unblinding events were documented and reviewed by the data monitoring committee. Otherwise, treatment codes remained concealed until study completion.

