## **Statistics**

All analyses were performed using IBM® SPSS® Statistics V25. Continuous variables were summarized using means and standard deviations. Categorical variables were expressed as frequencies and percentages. Paired *t* tests were used to evaluate differences in continuous variables. Chi-square ( $\chi^2$ ) tests were applied for comparisons of categorical variables. Survival outcomes were assessed using Kaplan–Meier analysis and Cox proportional hazards regression modelling. All tests were two-sided, and *p* values  $< 0.05$  were considered statistically significant.

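### Healing counts as primary success without confirmation, and no comparison of durable closure over all randomised participants is stated

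*Combined protocol and SAP*

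**What the plan says.** All the outcome rules are in the section Outcomes and Data Collection.

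- **Primary outcome:** it "was the proportion of wounds achieving complete healing within 24 weeks".
- **Definition of healing:** "Complete wound healing was defined as full re-epithelialization without drainage or dressing requirements". No second visit, minimum duration or confirmation step is attached.
- **Treatment-phase visits:** "Participants were evaluated weekly or biweekly for up to 24 weeks or until complete wound healing, whichever occurred first".
- **After healing:** "Participants who achieved wound healing were followed at 2- and 12-weeks post-healing to monitor for recurrence or complications".
- **Secondary outcomes:** these "included percentage reduction in wound area, wound recurrence rates, incidence and nature of adverse events", among others. No denominator or time point is given for recurrence.

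The Statistics section is generic. For categorical data it says "Categorical variables were expressed as frequencies and percentages" and that chi-square "tests were applied for comparisons of categorical variables". It does not link either statement to recurrence, and it describes no outcome that joins healing with remaining closed.

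**The concern.** The definition and the stopping rule for weekly or biweekly visits, read together, imply that success is fixed at the first visit at which the ulcer is judged closed. The document does not use those words; this is an inference. Nothing in the text then removes an ulcer from primary success if it is open two weeks later.

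The post-healing visits do look at durability, but only in those who healed. That is unavoidable and not a fault in itself. The difficulty lies in comparing the arms. Treatment can change who heals, so the healed participants in one arm need not resemble those in the other. A recurrence comparison restricted to them loses the protection of randomisation and can point away from the overall benefit. An outcome defined for everyone randomised (healed and still closed, yes or no) keeps that protection, and the document states no such comparison.

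At stake is whether a difference in healing can be read as a difference in lasting closure.

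**Working it through.** The document gives no healing rate, recurrence rate or sample size, so there is no figure of the plan's own to reproduce. **Every rate below is assumed.** The calculations show direction and range only.

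**1. Effect of reopening on the primary comparison**

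Proportion healed and still closed = H × (1 − r), where H is the proportion healed and r the proportion of healed ulcers that reopen. Assume H = 0.55 on product and 0.40 on placebo: difference 15 points, ratio 0.55/0.40 = 1.375.

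| Reopening, product vs placebo | Still closed | Difference (points) | Ratio |
|---|---|---|---|
| 5% vs 5% | 0.5225 vs 0.380 | 14.25 | 1.375 |
| 10% vs 10% | 0.495 vs 0.360 | 13.5 | 1.375 |
| 20% vs 20% | 0.440 vs 0.320 | 12.0 | 1.375 |
| 10% vs 5% | 0.495 vs 0.380 | 11.5 | 1.30 |
| 5% vs 10% | 0.5225 vs 0.360 | 16.25 | 1.45 |

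Equal reopening shrinks the difference and leaves the ratio alone. Small inequalities change the ratio modestly.

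Large inequalities do more. With 10% reopening on placebo, the arms are equal when 0.55 × (1 − r) = 0.36, so r = 1 − 0.36/0.55 = 0.345. Above about 34.5% on product, the direction reverses. Likewise, healing of 60% vs 40% with recurrence of 40% vs 10% gives 0.60 × 0.60 = 0.36 vs 0.40 × 0.90 = 0.36, so a 20-point difference disappears.

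**2. Recurrence among the healed can look worse while overall closure is better**

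Assume 40% heal in either arm and recur at 10%, and a further proportion g heal only on product and recur at r2.

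- Recurrence among the healed, product: (0.4 × 0.1 + g × r2)/(0.4 + g). Placebo: 0.10.
- Closed over all randomised, product: 0.36 + g × (1 − r2). Placebo: 0.36.

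| g | r2 | Recurrence among healed (placebo 10%) | Closed, all randomised (placebo 36%) |
|---|---|---|---|
| 0.1 | 0.3 | 14.0% | 43% |
| 0.1 | 0.4 | 16.0% | 42% |
| 0.2 | 0.3 | 16.7% | 50% |
| 0.2 | 0.4 | 20.0% | 48% |

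If r2 = 0.10, recurrence among the healed is 10% in both arms and nothing is distorted. If r2 = 0.05, the product figure is 9.0% (g = 0.1) or 8.3% (g = 0.2), slightly favourable.

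**3. The all-randomised measure alone can also mislead**

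Healing of 50% vs 40% with recurrence of 20% vs 10% gives 0.50 × 0.80 = 40% vs 0.40 × 0.90 = 36%. The composite favours the arm with twice the recurrence. The same counts arise with no harm to those who would heal either way, if the extra 10% recur at 60%: (0.4 × 0.1 + 0.1 × 0.6)/0.5 = 0.20. The data would be identical under either explanation.

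**4. Precision under the rates in step 3 (Newcombe 95% intervals, equal arms assumed)**

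| Comparison | Counts | Difference | 95% interval |
|---|---|---|---|
| Recurrence among healed, 50 per arm | 5/25 vs 2/20 | 0.10 | −0.130 to 0.304 |
| Recurrence among healed, 100 per arm | 10/50 vs 4/40 | 0.10 | −0.057 to 0.244 |
| Recurrence among healed, 200 per arm | 20/100 vs 8/80 | 0.10 | −0.008 to 0.201 |
| Healed and closed, 100 per arm | 40/100 vs 36/100 | 0.04 | −0.093 to 0.171 |

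All four intervals include zero.

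**The case against.** The strongest reply is that durability is already planned for. Recurrence is a named secondary outcome, two post-healing visits are scheduled, and general methods for categorical data are stated. If healed and recurred counts are published by arm, a reader can subtract one from the other and divide by the number randomised. This largely stands: the gap is one unstated derived comparison, not an absence of data. Subtraction does not, however, settle how missed visits and re-closed ulcers are counted.

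A second reply is that the recurrence denominator is not given. If it were all randomised participants, the arms compared would be the randomised ones. That also stands, which is why the selection argument is conditional. Only the observation is known to be limited to the healed.

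Third, the trial ran from January 2022 to June 2024, so any addition is post hoc. That is correct and limits what the additions can claim.

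A reader might infer more than the text allows:

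- *That any healing benefit would be spurious or would reverse.* The documents report no reopening rate, and a reversal needs a large imbalance.
- *That no durability was assessed.* The 2- and 12-week visits contradict this.
- *That a durable-closure analysis would show whether higher recurrence is harm or selection.* Step 3 of the working shows that it cannot.

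**Conclusion.** The point holds in a limited form. Healing is counted without confirmation, reopening at 2 weeks does not remove primary success, and no comparison of durable closure over all randomised participants is stated. Not stated is all that can be said: the document is a short summary, and if a fuller plan covers this, citing it would answer the point.

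The true size is unknown. Under the assumed 55% vs 40%, the effect on the primary ratio is modest for reopening of 5% vs 10% in either direction. The claim that the direction is safe holds only within that narrow range. The selection effect in step 2 depends on the extra healers recurring at a different rate from the rest; at the same rate there is none.

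This is a worthwhile and inexpensive improvement to the analysis. It is not a ground for setting aside the primary result.

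**What to change.** Keep the primary outcome as written. Add two analyses, labelled post hoc and exploratory, with all randomised participants in each arm as denominator:

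1. healed within 24 weeks and closed at the existing 2-week post-healing visit;
2. healed within 24 weeks and closed at the existing 12-week post-healing visit. This visit is the anchor because no week-24 visit is stated for a participant who healed earlier.

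Rules for both:

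- **Not observed to heal within 24 weeks**, including those lost, withdrawn or dead before healing: not closed.
- **Defining visit missed:** not closed in the lead version, with one sensitivity analysis counting it as closed. Only the visit that defines the analysis matters here.
- **Recorded as reopened and then re-closed, analysis 2:** not durably closed in the lead version, with a sensitivity analysis only where reopening was recorded. Two visits may not capture every reopening.

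Beside these, report recurrence among the healed by arm, with counts, denominator and a confidence interval for the difference, and note that it is a post-randomisation subset. The two measures together describe durability but do not separate recurrence harm from selection.

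Report completeness of the 12-week visit. A participant who heals at week 24 reaches it at week 24 + 12 = 36. As an illustration, suppose 10% of the healed in each arm missed the defining visit:

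- **12-week analysis, 42% vs 36% with full attendance:** 0.42 × 0.9 = 37.8% vs 0.36 × 0.9 = 32.4% (missed = not closed). Adding back 0.05 and 0.04 gives 42.8% vs 36.4% (missed = closed).
- **2-week analysis, healing 55% vs 40% with 5% reopening:** 0.55 × 0.95 × 0.9 = 47.0% vs 0.40 × 0.95 × 0.9 = 34.2%. Adding back 0.055 and 0.04 gives 52.5% vs 38.2%.

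**Cost:** a reanalysis of visits already scheduled, assuming closure status was recorded at them. The downsides are post hoc status, a somewhat lower healing rate, wide intervals and a little more analysis work.

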**A11002001**

**29 May 2025**

## **Study Protocol and Statistical Analysis Plan**

This multicentre, prospective, double-blind, two-arm, parallel-group randomized clinical trial was conducted between January 2022 and June 2024 to evaluate the efficacy of a topical probiotic formulation in a soybean concentrate compared with placebo in the treatment of diabetic foot ulcers (DFUs) (ClinicalTrials.gov Identifier: A11002001). Participants were randomized to receive twice-daily application of either investigational product (bottle A) or placebo (bottle B), both administered directly to the wound in addition to standard care. The contents of each bottle were prepared off-site, and both investigators and participants were blinded to treatment allocation.

The trial was conducted across three hospitals in Taiwan—Dalin Tzu Chi Hospital (Chiayi County), Taichung Tzu Chi Hospital (Taichung City), and Hualien Tzu Chi Hospital (Hualien City)—by three senior plastic surgeons, each with expertise in DFU wound management. The study was conducted in accordance with the principles of the Declaration of Helsinki (2013) and Good Clinical Practice guidelines. Ethics approval was obtained from the Institutional Review Boards of each participating centre. All participants provided written informed consent prior to enrolment. The trial was conducted and reported in accordance with the Consolidated Standards of Reporting Trials (CONSORT) guidelines.

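### Does the primary outcome need its own rule for ulcers closed by surgery?

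*Combined protocol and SAP*

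**What the plan says.** All the relevant text on the outcome is in the section Outcomes and Data Collection of the combined protocol and SAP.

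- The primary outcome "was the proportion of wounds achieving complete healing within 24 weeks".
- Healing is defined by end state: "Complete wound healing was defined as full re-epithelialization without drainage or dressing requirements". How the wound got there is not mentioned.
- The secondary outcomes end with "and the need for additional surgical intervention". The procedures are not listed, and no link to the primary outcome is given.
- Debridement is dealt with separately: "Debridement, when necessary, was performed as part of routine clinical care and recorded".
- On assessment: "Wound healing was assessed jointly by the treating plastic surgeon and wound care nurse". Independent blinded assessors were not used.

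The opening section says that the trial "was conducted between January 2022 and June 2024 to evaluate the efficacy of a topical probiotic formulation in a soybean concentrate compared with placebo", with both bottles "both administered directly to the wound in addition to standard care", and that it was run by "three senior plastic surgeons, each with expertise in DFU wound management". The Study Population section admits only ulcers without exposed bone or tendon. The Statistics section names chi-square tests for categorical variables, and Kaplan–Meier and Cox methods for survival outcomes, which it does not define further. It says nothing about surgery during follow-up.

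**The concern.** The stated aim is the efficacy of a topical product. If the treating surgeon grafts or directly closes an ulcer in week 10 and the skin is intact in week 16, the wound meets the healing wording although the product may have contributed nothing. The same ulcer would also count under the surgical secondary outcome. The plan foresees some further surgery, plastic surgeons ran the sites, and the treating surgeon shared in judging healing, so the case is not far-fetched.

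Two things would be at stake. If operations fall mainly on ulcers that would otherwise stay open, and do so at the same rate in both arms, crediting them as healed dilutes a real effect and costs power. If the rates differ between arms, the observed difference can move in either direction. If the survival analysis is of time to healing, the same question arises there.

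**Working it through.** **No figure to reproduce.** The documents give no sample size, healing rate, effect size or surgery rate. Everything below is an illustration on assumed inputs.

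**Assumed inputs.** Healing without surgery p1 = 0.50 (product) and p2 = 0.35 (placebo); n = 170 per arm; two-sided 5% test. Let s be the share of would-be non-healers closed surgically by week 24, and h the share of would-be healers operated on before they heal.

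**Formulas.**
- Definition as written: q = p + (1 − p)s. With equal s, the difference is (p1 − p2)(1 − s).
- Alternative, operated ulcers counted as not healed: q = p(1 − h). With equal h, the difference is (p1 − p2)(1 − h).
- Power = Φ{[d − 1.96√(2q̄(1 − q̄)/n)] / √([q1(1 − q1) + q2(1 − q2)]/n)}, where d = q1 − q2 and q̄ is the mean of q1 and q2.

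With no surgery, d = 0.15 and q̄ = 0.425, so power = Φ[(0.150 − 0.105)/0.053] = 0.80.

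**Equal rates in both arms.**

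| s or h | Difference, either rule (points) | Power, as written (s) | Power, not-healed rule (h) |
|---|---|---|---|
| 0 | 15.0 | 0.80 | 0.80 |
| 2% | 14.7 | 0.78 | – |
| 5% | 14.25 | 0.75 | 0.77 |
| 10% | 13.5 | 0.70 | 0.73 |
| 20% | 12.0 | 0.60 | 0.65 |
| 30% | 10.5 | 0.51 | 0.56 |

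Both rules shrink the difference by the same kind of factor. Which has more power depends on how s compares with h. The not-healed rule is ahead only while h stays below about 2.7%, 6.6%, 13%, 25% and 37% for s = 2%, 5%, 10%, 20% and 30%.

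**Type I error.** With 40% healing in both arms, simulated rejection was 0.047 to 0.054 for equal s from 0 to 0.3 as written, and 0.050 to 0.053 for equal h of 0, 0.1 and 0.2 under the alternative. Neither rule inflates it.

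**Unequal rates (product / placebo).**

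| Rates | As written | Counted as not healed |
|---|---|---|
| 10% / 20% | 55.0% − 48.0% = 7.0 points | 45.0% − 28.0% = 17.0 points |
| 20% / 10% | 60.0% − 41.5% = 18.5 points | 40.0% − 31.5% = 8.5 points |

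The two rules are about equally sensitive and move in opposite directions. Changing the rule does not remove the sensitivity.

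**Is the outcome computable from the text?** Yes. An ulcer that is fully covered, dry and free of dressings by week 24 is healed, whatever care it received. An ulcer removed by amputation has not itself re-epithelialized, so on a plain reading it is not healed. An analyst can classify every wound without a further rule.

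**The case for a change.** The strongest case for a change is that the text can be read in two ways. One reader takes re-epithelialization to mean closure by the wound itself; another accepts any intact skin. Surgery was expected, since it is an outcome, and the person who might operate also helped judge healing. If closures were common, the primary result would describe the whole care package more than the product, and a reader could not see this without a count by arm. The occurrence of surgery had to be captured for the secondary outcome, so asking for the count costs little.

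Much of this stands. The wording is silent, and a sentence on classification with a count by arm would help a reader of the results. It does not show that the planned analysis is wrong or worse than another. Further surgery is undefined in the plan and could mean operative debridement or amputation. Grafts, flaps and direct closure are not mentioned anywhere, and excluding exposed bone or tendon may make them less likely. Investigators and participants were blinded, so a difference in surgery rates would have to arise by chance or through the product's own effect, and the latter belongs in a treatment-policy comparison. The trial ran to June 2024, so unless a dated earlier rule exists, a not-healed definition brought in now would be post hoc. It would also make the primary outcome depend partly on discretionary decisions to operate.

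**Conclusion.** The gap in wording is real, but no change to the plan follows. As written, the definition gives a computable and defensible outcome: wound status at 24 weeks under the assigned topical product plus standard care. Equal surgery rates leave type I error intact. The alternative rule is a trade-off, since it gains power only when would-be healers are seldom operated on and is no more stable when rates differ between arms.

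The size is unknown. Under the assumed 50% vs 35% and 170 per arm, equal closure of 2% of would-be non-healers costs 0.3 points and about 0.02 of power, while 20% costs 3.0 points and about 0.20. If no ulcer was closed surgically, nothing changes. How such ulcers were classified, and how many there were in each arm, belongs in the results report. An analysis counting them as not healed is optional, and should be labelled post hoc unless a dated rule already exists.

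This conclusion rests on surgical closure having been uncommon or similar between arms. The documents neither support nor contradict that.

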## **Statistics**

All analyses were performed using IBM® SPSS® Statistics V25. Continuous variables were summarized using means and standard deviations. Categorical variables were expressed as frequencies and percentages. Paired *t* tests were used to evaluate differences in continuous variables. Chi-square ( $\chi^2$ ) tests were applied for comparisons of categorical variables. Survival outcomes were assessed using Kaplan–Meier analysis and Cox proportional hazards regression modelling. All tests were two-sided, and *p* values  $< 0.05$  were considered statistically significant.

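### Percentage wound-area reduction is capped at +100% with no lower limit, yet only mean, SD and a t test are planned, so a few enlarging ulcers can dominate it in small to moderate arms

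*Combined protocol and SAP*

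**What the plan says.** Under Outcomes and Data Collection, the secondary outcomes "included percentage reduction in wound area, wound recurrence rates, incidence and nature of adverse events", plus the need for further surgery. Percentage area reduction is the only one of these that is naturally continuous. Its raw data are described in the same section: "At each visit, wound surface areas were measured and documented using standardized digital photography". The primary outcome is "the proportion of wounds achieving complete healing within 24 weeks".

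Study Population admits "a non-healing DFU measuring greater than 1 cm 2 in area". The full criteria are in a table that is not in the text available for review, so nothing is inferred here about an upper size limit.

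Under Statistics, the summary rule is "Continuous variables were summarized using means and standard deviations" and the test rule is "Paired *t* tests were used to evaluate differences in continuous variables". The section names no median, rank test, transformation, floor for enlarged wounds or sensitivity analysis. Nor does it say how an enlarged ulcer is scored.

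**The concern.** Percentage reduction is a lopsided scale. Complete healing gives +100% and nothing can exceed it, so all healed ulcers tie at that value. Enlargement has no limit below, and a small starting area makes a modest absolute increase look extreme. The result is a spike at the top and a possible long negative tail. A mean on such a scale can be set by the few worst ulcers, often those with the smallest baseline, and the SD then describes neither the spike nor the tail.

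At stake is the trial's graded efficacy measure. It could miss a real benefit, or appear to disagree with the healing proportion, because of how the scale treats a handful of participants. This is a different matter from the paired form of the named test, and it would remain if that test were replaced by an unpaired one.

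**Working it through.** The plan states no sample size, effect, SD or power for this outcome, so there is no figure to reproduce. Arm sizes (1:1), healing rates and the frequency of enlargement below are all assumptions. All tests are unpaired and two-sided at 0.05.

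**1. The scale.** The usual definition is 100 × (A0 − At)/A0, with A0 the baseline and At the later area; the plan gives no formula.
- At = 0 gives +100, the maximum.
- 1.1 to 2.2 cm² gives −100; 1.1 to 3.3 cm² gives −200; 1.5 to 6.0 cm² gives −300.
- 10 to 12 cm² gives only −20.

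**2. Leverage on one arm.** If k of n ulcers take the value v in an arm with mean m, the mean shifts by k(v − m)/n. Take m = 75, SD 30, k = 1 and v = −200:

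| n per arm | Shift in mean | New SD |
|---|---|---|
| 20 | −275/20 = −13.8 | 68.4 |
| 30 | −275/30 = −9.2 | 58.5 |
| 50 | −275/50 = −5.5 | 49.1 |
| 100 | −275/100 = −2.8 | 40.7 |

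For n = 30 the SD follows from variance = [29 × (30² + 75²) + 200²]/30 − 65.83² = 3,307, times 30/29, whose square root is 58.5.

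**3. Stress test, one bad ulcer placed in the better arm.** Healed 65% v 40%, unhealed uniform on 0 to 95%, 4,000 runs. The true difference is (0.65 − 0.40) × (100 − 47.5) = 13.1 points. Power in the correct direction:

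| n per arm | t test, none → one at −200% | Rank test, none → one at −200% | Sign of mean difference reversed |
|---|---|---|---|
| 30 | 35% → 0.4% | 43% → 31% | 32% |
| 50 | 54% → 7% | 65% → 56% | 12% |
| 100 | 82% → 49% | 91% → 88% | 1% |

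A milder ulcer (−50%) at 100 per arm moves the average difference only from 13.1 to 11.8.

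**4. Enlargement at random in both arms.** In the same model, 3% of ulcers score −100% to −400%. Power for the t test v the rank test is 17% v 39% (n = 30), 22% v 60% (n = 50) and 32% v 87% (n = 100). With no true difference, rejection is 3% to 5% for both tests.

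**5. A second model, benefit partly through healing.** 50 per arm, healed 50% v 30%, unhealed area ratio log-normal with median 0.5 v 0.7, 3,000 runs:

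| Log-SD | Welch t | Rank |
|---|---|---|
| 0.6 | 81% | 80% |
| 0.8 | 65% | 72% |
| 1.0 | 48% | 67% |
| 1.2 | 32% | 63% |

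Mean and rank comparisons point in opposite directions in about 3% of trials at log-SD 1.0 and 6% at 1.2.

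**6. The same model, benefit only in unhealed ulcers.** 40% healed in both arms, median ratio 0.4 v 0.7:

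| Log-SD | Welch t | Rank | Loss with ranks |
|---|---|---|---|
| 0.4 | 76% | 59% | 17 |
| 0.6 | 60% | 35% | 25 |
| 0.8 | 44% | 23% | 21 |
| 1.0 | 30% | 17% | 13 |
| 1.2 | 19% | 13% | 6 |

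A repeat gave 61% v 34% at 0.6 (27 points) and 30% v 15% at 1.0. With 60% healed in both arms it is 36% v 11% at log-SD 0.6.

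**The case against.** The strongest objection is that ranks are not a free improvement. Benefit without closure is exactly what a graded outcome adds to a healing proportion, and step 6 shows the rank test performing worse there, because it discards how far below 100% an unhealed ulcer sits. The median has its own ceiling: once more than half of an arm heals, it is 100%. A reader might infer from steps 3 to 5 that the mean and t test should simply be replaced at almost no cost in power. The calculations do not support that, and this part of the objection stands in full.

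The size of the problem can also be challenged. Step 3 puts the bad ulcer in the better arm by design. In step 5 the clear gain starts at log-SD 0.8. There the chance that an unhealed ulcer ends larger than baseline is 19% in one arm and 33% in the other, or (25 × 0.19 + 35 × 0.33)/60 = 27% overall. The documents give no such frequency. In that model no trial of 3,000 produced a significant t test in the wrong direction. This stands as a limit on magnitude. It does not remove the point: step 4 places enlargement at random, and log-SD 0.8 implies only about 1.5 tripled ulcers among 100 participants.

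Finally, the plan never assigns this outcome to the t test by name, and the named test is paired, so it is not a between-arm comparison. That is true and is a separate defect, arguably a more serious one. But the rule is the only one given for continuous variables, and the simulations already assume an unpaired test.

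**Conclusion.** The point holds as a cheap improvement to the analysis of one secondary outcome. With about 20 to 50 per arm, one or two ulcers that triple in area or worse can dominate the arm means and cost much of the power of a mean-based comparison. The effect of a single such ulcer weakens near 100 per arm, and mild enlargement matters little. All magnitudes rest on assumed arm sizes, healing rates and enlargement frequencies.

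Three stronger readings are not supported. The t test does not give excess false positives: null rejection stayed at about 3% to 5%. The primary healing proportion is not affected. And nothing in the documents shows that enlarging ulcers actually distorted this trial's results. The plan simply offers no way for a reader to tell.

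**What to change.** For percentage area reduction, amend the Statistics section to:
- state a between-arm comparison, with the mean difference and its 95% CI;
- report median and interquartile range by arm as well as mean and SD;
- add a Wilcoxon-Mann-Whitney comparison as a robustness analysis, with healed ulcers tied at the top rank and enlarged ulcers ranked lowest in order of enlargement;
- report the probability that a probiotic participant does better than a placebo participant, with its 95% CI, beside the mean difference.

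The document is dated May 2025 and the trial ran to June 2024, so the addition should be labelled post hoc if results were already known.

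The cost is a few sentences and one extra analysis; the areas are already recorded at each visit. The downside should be stated with the result. The rank analysis may be the weaker one when healing is similar in both arms, and the median is uninformative once more than half of an arm has healed. That is why it belongs beside the mean and not in its place.

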## **Randomization and Intervention**

Block randomization in blocks of 8 was used to assign participants to 1 of 2 groups: Group 1 received bottle A (topical probiotic in soybean concentrate) and Group 2 received bottle B (placebo). Both groups received secondary dressing with standard wound care with wet-to-dry dressings. The assigned topical treatment was applied directly to the ulcer twice daily throughout the treatment phase.

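### The only test named for continuous variables is a paired t test, which does not fit two unmatched arms and leaves wound-area reduction without a stated between-arm comparison

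*Combined protocol and SAP*

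**What the plan says.** The introduction sets out the design: "This multicentre, prospective, double-blind, two-arm, parallel-group randomized clinical trial was conducted between January 2022 and June 2024". Under Randomization and Intervention, allocation is described thus: "Block randomization in blocks of 8 was used to assign participants to 1 of 2 groups". Neither section mentions matching, crossover or a control wound on the same person.

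Under Outcomes and Data Collection, the primary outcome "was the proportion of wounds achieving complete healing within 24 weeks". The secondary outcomes "included percentage reduction in wound area, wound recurrence rates", together with adverse events and further surgery. Wound characteristics were taken at enrolment, and at each visit "wound surface areas were measured and documented using standardized digital photography".

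Under Statistics, the summary is given as: "Continuous variables were summarized using means and standard deviations". The one test for differences in such variables follows: "Paired *t* tests were used to evaluate differences in continuous variables". The section also names chi-square tests for categorical variables, and Kaplan–Meier and Cox methods for survival outcomes. Tests are two-sided at 0.05.

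**The concern.** A paired t test analyses differences between the two members of a natural pair. A probiotic participant and a placebo participant are not such a pair, and assignment within blocks of 8 does not make them one. Percentage reduction in wound area gives one value per wound, with no partner in the other arm.

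A reader therefore could not tell what a p value for this outcome means. There are three possibilities:

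- **Within-arm test.** It tests change from baseline, which standard care alone can produce, and does not estimate product versus placebo.
- **Paired test across arms.** The p value depends on the arbitrary order of the rows.
- **Wording slip.** The analysis may be sound, but it is wrongly described.

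**Working it through.** The document gives no sample size, SD or power figure, so there is nothing of its own to reproduce. The check has two parts: a comparison of methods with outcomes, which rests on the text, and an illustration, in which every input is assumed.

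**1. Does any named method compare percentage area reduction between arms?**

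| Method in Statistics | Use | Compares this outcome between unmatched arms? |
|---|---|---|
| Mean and SD | Description | No, not a test |
| Paired t test | Differences in continuous variables | No, there are no pairs across arms |
| Chi-square | Categorical variables | No |
| Kaplan–Meier, Cox | Survival outcomes | No |

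No independent-samples test, ANCOVA, mixed model or rank test is named.

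**2. Within-arm reading.** Suppose the true change is identical in both arms and each arm's paired test has power p. The chance that exactly one arm is significant (a split) is 2p(1−p):

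- p = 0.50: 2 × 0.50 × 0.50 = 50%
- p = 0.80: 2 × 0.80 × 0.20 = 32%
- p = 0.95: 2 × 0.95 × 0.05 = 9.5%
- p = 0.99: 2 × 0.99 × 0.01 = 2.0%

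A direct independent-groups test would reject in about 5%. By the noncentral t distribution, the split falls to about 5% once the within-arm change reaches roughly 0.74 SD at n = 30 per arm, or 0.63 SD at n = 40.

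To see where wound data might lie, assume a healed share h at 100% reduction and the remaining wounds uniform from a to 100%. The mean is 100h + (1−h)(a+100)/2. For h = 0.30 and a = 0:

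- mean = 30 + 0.70 × 50 = 65
- mean square = 0.30 × 10,000 + 0.70 × 3,333 = 5,333
- variance = 5,333 − 4,225 = 1,108, so SD = 33.3
- standardised change = 65/33.3 = 1.95

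The same steps give the other cells. Splits come from simulation with identical arms, 20,000 trials per cell; each entry runs over h = 30 / 50 / 70%.

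| Unhealed wounds spread over | Change in SDs | Split, n = 30 | Split, n = 40 |
|---|---|---|---|
| 0 to 100% | 1.95 / 2.32 / 3.05 | 0 / 0 / 0% | 0 / 0 / 0% |
| −50 to 100% | 0.95 / 1.29 / 1.86 | 0.22 / 0 / 0% | 0.03 / 0 / 0% |
| −100 to 100% | 0.45 / 0.77 / 1.26 | 46.0 / 5.9 / 0.03% | 34.4 / 1.3 / 0% |

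In the first two rows both arms are significant in 99.8 to 100% of trials although the product adds nothing. The Welch test between arms rejects in 4.7 to 5.4% across all cells.

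**3. Across-arm reading.** With arbitrary pairs, the degrees of freedom fall from 2n−2 to n−1. The error rate stays near nominal (4.8 to 5.3% in the same simulations), but the p value depends on the pairing. I took 60 datasets at each n with a Welch p of 0.045 to 0.055 (50% versus 35% healed, the rest uniform from −50 to 100%) and re-paired each 2,000 times. The central 95% of paired p values ran, as a median over datasets, from 0.018 to 0.094 at n = 30 and from 0.021 to 0.088 at n = 40. About 42% of pairings fell below 0.05.

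**The case against.** The strongest reply is that the sentence never says the differences are between groups. Wound area was measured repeatedly, so valid within-participant pairs exist, and a paired test suits them. On that reading the fault is an omission rather than a wrong test. This is a fair reading, but it does not close the gap: the stated aim is efficacy compared with placebo, and a within-arm test does not address that.

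A second reply is that little depends on it: one secondary outcome is affected, the document reports no results, and the illustration rests on assumed inputs. Most of this stands. In most of the modelled cells the split is essentially zero, and the 34 to 46% figures need only 30% healed together with unhealed wounds spread as far as a doubling in area. Pairing across arms also needs equal arm sizes, which are not stated, and it does limited harm: with identical arms, paired and Welch decisions disagreed in only 1.4 to 1.8% of simulated trials. The 0.02 to 0.09 swing comes from datasets chosen to lie near the threshold.

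Third, no time point is given for percentage reduction. That is correct, and it is a separate gap. It does not prevent the test from being corrected, although any re-run has to state the time point it uses.

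**Conclusion.** The concern holds. As written, the plan gives no proper between-arm test of percentage wound-area reduction, and the one test it names for continuous variables does not fit unmatched parallel arms. That conclusion rests on the text alone.

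It should be fixed, but its reach is limited. It does not show that the comparison actually run was invalid, because the document does not reveal which test that was. The primary proportion, tested by chi-square, and the Kaplan–Meier and Cox analyses stand.

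The size is hypothetical. The likelier harm is one of interpretation: under the milder assumptions, a significant within-arm reduction would appear almost always for an inert product. Large splits between arms are not the likely case.

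**What to change.** First state which test was run and what was paired.

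- **Independent-samples test:** correct the sentence to say so. Cost: one sentence.
- **Paired test:** replace the sentence with the following.

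> Continuous outcomes are compared between arms by an independent-groups test (mean difference with 95% CI); paired tests describe within-arm change only and support no treatment claim.

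Then re-run percentage wound-area reduction on that basis, state the time point used, and label the result post hoc, because the trial ended in June 2024 and the document is dated 29 May 2025. Cost: the wording plus one re-run in the same software, with no new data.

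ANCOVA adjusting for baseline wound area and a rank-sum check (healed ulcers all sit at 100%) would be useful additions, but neither is needed to cure the error.
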